7.4 Special Populations to Consider

This study is likely to enroll persons involved in the criminal justice system who are receiving HIV care at participating sites. The study will not recruit persons incarcerated/detained in a correctional facility or currently considered "prisoners" by local or state laws, but will not exclude parolees or probationers. At screening, prisoner status will be assessed using a streamlined

assessment based on the definition of a prisoner in 45 CFR 46.303(c). Throughout the study, prisoner status will be documented on the Criminal Justice case report form (CRF).

Those participants who become incarcerated during the course of their involvement with this study will continue to be followed to ensure safety and data integrity. All study interventions (XR-NTX or TAU) will be discontinued while the participant is incarcerated. If necessary for safety and with the permission of the participant, correctional facility officials will be informed of study participation. When possible, participants will be contacted to complete questionnaires and surveys, which would include safety checks. These visits can occur over the telephone or as in-person visits, whichever is more appropriate for the local research site and the correctional facilities' policies. The visits will only occur if confidentiality can be maintained. This generally assumes that in-person visits will be done in private rooms and that recording equipment (regardless of type of visit) can be turned off or destroyed. No biospecimens will be collected (blood or urine) during any visit that occurs with an incarcerated prisoner. If necessary, specific documents for incarcerated participants will be developed and approved by the IRB of record. All local guidelines will be followed, including any required reporting to the IRB or other institution when a participant becomes incarcerated. Despite the use of a central IRB for this study, local IRBs may be notified if a participant becomes incarcerated. Appropriate progress notes will be written to ensure complete documentation of any interaction with an incarcerated participant, specifically mentioning confidentiality procedures.

An Office for Human Research Protections (OHRP) Prisoner Research Certification Letter will be filed through the IRB of record and distributed to the sites that cede review. Sites that are not ceding review to the IRB of record will be responsible for obtaining an OHRP Prisoner Research Certification Letter. Local sites will be covered by the OHRP Prisoner Certification to enable follow-up of study participants who may become incarcerated.

Number of Sites

No more than eight HIV outpatient clinics will serve as sites for this study.

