9.2 Treatment Conditions

9.2.1 HIV Usual Care (Both Arms)

All participants will receive comprehensive HIV primary care, case management, addiction counseling, and social support services from HIV clinics as they would regardless of study participation. As part of protocol training, HIV clinic providers will be encouraged to offer ART within 4 weeks of randomization for participants not already prescribed ART. Current guidelines recommend offering ART to all HIV-infected participants, regardless of CD4 count [35]. The schedule of medical care provided will be as deemed appropriate by the treating provider. HIV-infected participants are typically seen at least twice within the first month of initiating ART, and at least every 3 months thereafter for monitoring. Medical visits will not be considered study visits, though they may coincide with study visits. HIV clinic treatment will also include usual addiction counseling services, which are offered as a part of usual care in most large U.S. HIV clinics. As part of protocol training, HIV clinic providers will be asked to refer study participants to existing addiction counseling services in their clinic, as they would do regardless of study participation. Throughout the course of the trial, HIV clinics will be monitored for any potential changes that might occur in standard practice around medical management of HIV infection or addiction treatment services. Throughout study participation, HIV clinic medical visits will be tracked through medical record abstraction, and counseling visits will be tracked through participant self-report (See Section 10, Assessments).

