9.2.2 Medical Management (when applicable)

Study clinicians will be trained in medical management (MM). MM is a brief counseling intervention delivered by non-addiction medical providers to improve response to medication-assisted addiction treatments delivered in medical settings [129] [130]. It has augmented care for medication-assisted treatment of alcohol dependence with acamprosate and oral naltrexone in the COMBINE study [131], integration of XR-NTX treatment of alcohol dependence in primary care settings [36], and integration of BUP/NX for treatment of opioid dependence in primary care [132]. Since MM is meant to facilitate medication-assisted addiction treatment, it will be performed only for participants offered medication-assisted treatment in the HIV clinic (e.g., participants with opioid use disorders randomized to XR-NTX and TAU participants receiving clinic-based buprenorphine/naloxone or methadone for opioid use disorder). TAU participants referred for off-site methadone maintenance or buprenorphine/naloxone will not receive MM since medical

oversight is the responsibility of the treating provider. TAU participants who receive non-medication-assisted treatments such as 12-step groups or psychosocial counseling will not receive MM. During brief MM sessions, study clinicians will review recent drug and alcohol use, recommend abstinence, review medication side effects, and encourage adherence to medication-assisted treatment and participation in clinic and/or community support groups.

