Among the 9 individuals in the pilot study who had opioid use disorder and were unsuppressed at baseline, 6 (17%) of the 36 subsequent viral load values were missing. In the pilot, viral load was measured monthly, increasing the opportunity for missing data, whereas CTN-0067 collects follow-up viral loads only at 12 and 24 weeks and will likely have fewer missing viral loads. The primary outcome analysis will be carried out using the binary repeated measures of viral load (RMVL) framework of Rose et al., a type of time series model. In theory, time series models can accommodate missing data better than non-longitudinal models by using all non-missing data points. However, this approach assumes that missing data are not informative, that is, that missing values are probably similar to corresponding non-missing values with the same set of other predictors. For substance-use trials, missing at random (MAR) is less likely than missing not at random (MNAR) alternative: if data are missing, it is probably because the participant is unsuppressed. So, for the primary analysis, “unsuppressed” will be substituted for missing suppression status values. Since death is at least as undesirable as lack of suppression, “unsuppressed” will be assigned as a status value for visits subsequent to death. A secondary sensitivity analysis will explore the extent to which trial conclusions need to be changed as the missingness assumption approaches MAR.

9.2.3.4 *Dispensing of XR-NTX*

Study medication (XR-NTX) will be provided by the study at no cost to the participant. XR-NTX will be administered in clinic at the Treatment Initiation Visit and at treatment weeks 4, 8, 12, 16 and 20.

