9.2.4 Treatment as Usual (TAU)

Participants assigned to the TAU group will receive the standard treatment for opioid use disorder provided at each HIV clinic. The standard of care in U.S. HIV clinics is currently to link with opioid agonist treatment services. Opioid substitution therapy is recommended for HIV-infected participants with opioid dependence [35, 104], and many HIV practices are being encouraged to adopt clinic-based BUP/NX [105]. Assessment of TAU includes assessing use of medication-assisted treatments for alcohol use disorder as well as opioid use disorder since we anticipate some participants with OUD will also have AUD. TAU assessment will also include characterization of usual counseling services and linkages with local detox programs available at each site.

Many HIV clinics receive funding from the Ryan White Care Act for case management and addiction/mental health counseling services to facilitate engagement of HIV-infected patients with substance use disorders in treatment. In a 6-month randomized trial of methadone maintenance referral strategies, passive referral of heroin users resulted in 8% methadone maintenance enrollment at 6 months vs. 29% enrollment among those randomized to case-management assisted referrals ($p = .006$) [139].

During the formal site selection process, a thorough assessment will be conducted of each site’s standard practice for linkage to addiction treatment services. Throughout the course of the trial, HIV clinics will be monitored for any potential changes that might occur in standard practice around linking HIV-infected clinic patients to substance use treatment.

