17.4 Sample Size and Duration of Recruitment Phase

The CTN-0067 CHOICES scale-up trial will randomize 350 participants with opioid use disorder who are unsuppressed at baseline from no more than 8 sites over approximately 22 months for a power of 80%. Justification for this decision follows.

The trial will be powered as a non-inferiority trial since the overall goal of the research is to add to rather than to supplant the available effective opioid agonist treatment options currently available.

17.5 Substantive Justification for a Non-Inferiority Design.

A non-inferiority trial and the attendant choice of margin must be justified not just statistically, but also on substantive grounds. A non-inferiority trial design is justified when the active control is well-established and effective, and when a non-active control would be unethical, as in the case of treatments for HIV infection [165]. Both conditions are salient to the CTN-0067 CHOICES scale-up study in that opioid agonist therapy with buprenorphine or methadone is considered the standard of care for treatment of opioid dependence in HIV infected patients [104], and placebo treatments for either opioid use disorder or HIV infection are unethical.

Reporting of non-inferiority methods must include [165, 166]:

- Non-inferiority margin (delta)
- Sample size calculation must take into account the margin
- Both ITT and per-protocol analyses must be presented
- Confidence intervals for the results must be presented
- Justification of the margin

The first 4 points have been addressed in other parts of this statistical section. The following section describes the justification for the margin.

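### Section 7.4 stops TAU as well as XR-NTX during incarceration; read literally, this withdraws usual-care methadone or buprenorphine on account of the study, so the sentence should be reworded

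*Combined protocol and SAP*

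**What the plan says.** Section 7.4 covers participants who are incarcerated after enrolment. They stay in follow-up, but "All study interventions (XR-NTX or TAU) will be discontinued while the participant is incarcerated". The rest of the section allows facility officials to be told of study participation if safety requires it and the participant agrees. It permits questionnaires and safety checks by telephone or in person, and it bars collection of blood or urine in custody. It also provides for IRB-approved documents for incarcerated participants if they are needed, and requires local guidelines to be followed. The OHRP certification is described as serving follow-up.

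Section 9.2.4 defines the comparator: "Participants assigned to the TAU group will receive the standard treatment for opioid use disorder provided at each HIV clinic". Section 17.5 rests the non-inferiority design on the statement that "opioid agonist therapy with buprenorphine or methadone is considered the standard of care for treatment of opioid dependence in HIV infected patients".

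On supply and oversight, section 9.2.3.4 says "Study medication (XR-NTX) will be provided by the study at no cost to the participant" and makes no matching statement for agonist medication. Section 9.2.2 gives study-clinician medical management (MM) to "TAU participants receiving clinic-based buprenorphine/naloxone or methadone for opioid use disorder". It withholds MM from those referred off site, because there medical "oversight is the responsibility of the treating provider".

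**The concern.** A protocol may suspend what the study itself delivers. It should not direct that ordinary clinical care stop because the patient is a participant. Section 7.4 places TAU under study interventions and discontinues it together with XR-NTX, without separating the study-delivered parts of the TAU condition from the medication that a clinic or outside programme prescribes as usual care.

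What is at stake is continuity of agonist treatment for a TAU participant who is jailed, and only for the period of incarceration. The situation is foreseeable. Section 7.4 expects to enrol people with criminal-justice involvement and does not exclude parolees or probationers, and section 7.3 lists people leaving local criminal justice systems as a recruitment target.

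**Working it through.** No arithmetic applies; the point does not depend on the margin, alpha, power or sample size. The check sets the sections side by side.

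1. **Scope of the rule.** The sentence in 7.4 is mandatory, covers all study interventions and names TAU in its parenthesis. It has no qualifier for agonist treatment.

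2. **What TAU contains.** Under 9.2.4 it is each clinic's standard treatment for opioid use disorder, described there mainly as linkage to agonist services. Section 17.5 names buprenorphine or methadone. Stopping TAU therefore includes, on its face, stopping these drugs.

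3. **Who controls the medication.** The only drug that the protocol says the study provides is XR-NTX (9.2.3.4). Oversight of off-site methadone or buprenorphine/naloxone lies with the treating provider (9.2.2). For off-site treatment the rule thus reaches care that the study neither supplies nor oversees.

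4. **What in TAU is study-delivered and can properly pause.** Two parts qualify: medical management for clinic-based buprenorphine/naloxone or methadone (9.2.2), and the study clinician's Treatment Plan, which covers methadone and buprenorphine and is reviewed at weeks 4, 8, 12, 16, 20 and 24 (12.6).

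5. **Search for an exception.** None is found in the rest of 7.4. The other stopping provisions (9.6, 23.2, 23.9, 24.2.5.3 and 24.2.5.4) do not supply one either. Two places draw the line that 7.4 misses: 24.2.5.4 has a positive pregnancy test stop study medication, and 12.8 lists the study intervention or medication separately from treatments received under TAU.

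6. **Fit with usual care.** Section 9.2.1 has participants in both arms receive usual services, including "addiction counseling, and social support services from HIV clinics as they would regardless of study participation". That text does not name agonist medication, so it cannot serve as an exception, but a rule that stops TAU in custody sits badly with it.

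7. **Consequence of the literal text.** Section 19.2 classes any departure from protocol requirements as a deviation. On the literal wording, a site that helped to continue a jailed participant's buprenorphine could be recorded as deviating.

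**The case against.** The strongest defence is intent. Section 16.0 uses XR-NTX and TAU as labels for the two study conditions, so the sentence can be read as pausing delivery of either assigned condition. Contact in custody is limited to questionnaires and safety checks, and the OHRP certification is there to allow follow-up. Sections 9.2.1, 9.2.2 and 17.5 all suggest that the protocol does not mean to withdraw usual care. The provision for custody-specific IRB documents, or the Manual of Operating Procedures, may settle the matter; neither is in the file. This reading is plausible and probably right about intent. It does not change what the sentence says, and neither the if-necessary provision nor the local-guidelines sentence exempts agonist treatment.

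The defence is also right about mechanism. A reader might infer that participants' methadone would in fact be stopped. The documents do not support that: the Treatment Plan sets out what the participant should engage in, nothing in it tells a study clinician to end another provider's prescription, and 7.4 does not provide for plan review in custody.

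A reader might also infer that those harmed could be counted from scheduled forms. Section 10.1 lists the Criminal Justice form at baseline and weeks 12 and 24, and buprenorphine and methadone chart abstraction at weeks 4, 8, 12, 16, 20 and 24. These could show incarceration and charted treatment. They are not shown to record why treatment stopped or what a jail provided, so they cannot be relied on to identify treatment stopped because of the study.

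**Conclusion.** The sentence is wrong as written and should be corrected. It states a rule that, followed exactly, withdraws standard treatment because of study participation. The correction is minor: it concerns only the period of incarceration, the frequency is unknown because no incarceration rate is given, and no actual stopping of treatment is shown.

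A reader might go further and infer that removing TAU in custody weakens the comparator and so favours a non-inferiority finding. The documents do not support this. The rule applies to both arms, missing viral loads are imputed by the same rule in both arms (17.10), and nothing gives the number or distribution of jailed participants. No effect on power, type I error or the primary result is claimed.

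The conclusion rests on the protocol text alone, and assumes that no document outside the file formally overrides 7.4. If such a document exists, the protocol sentence should still be brought into line with it.

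**What to change.** Replace the sentence in section 7.4 with:

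*Study-supplied XR-NTX, study-delivered medical management and study Treatment Plan reviews will be suspended while the participant is incarcerated. Usual-care treatment for opioid use disorder, including methadone or buprenorphine, remains with the treating clinicians and the correctional facility and is not to be stopped on account of the study.*

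Leave the surrounding sentences on follow-up, questionnaires, safety checks and biospecimens unchanged. The new text keeps the likely intent and names the parts that pause.

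The cost is one sentence replaced by two in a protocol amendment, with IRB approval. No visit, data field or analysis changes.

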7.5 Site Characteristics

HIV clinics will be selected primarily on the basis of the following characteristics:

- 1)** Provide HIV primary care.
- 2)** Have a sufficient population of potential participants to achieve study enrollment goals.
- 3)** Have providers willing to be trained in use of XR-NTX for management of opioid use disorder.
- 4)** Capable of prescribing ART to participants, regardless of CD4 count.
- 5)** Access to addiction counseling services as part of usual care.
- 6)** Clinic offers access to opioid agonist treatment, either on-site or by referral.

We will specifically target HIV clinics in areas that have local prevalence of untreated opioid use disorder and HIV that support feasibility of enrollment.

7.6 Rationale for Site Selection

Sites that have access to an adequate number of HIV-infected participants with suboptimally controlled HIV and untreated opioid use disorder will be selected for participation. In order to achieve target enrollment for this study, we anticipate that most (but not all) participating HIV clinics will need to see $\geq 1,000$ unduplicated HIV-infected potential participants per year. This number is based on enrollment rates observed in the pilot study and experience of CHOICES pilot study investigators in enrolling subjects in the BHIVES study [29]. We have also included site selection criteria that attempt to limit site variability in treatment effects (e.g., capacity for prescribing ART regardless of CD4 count; access to addiction counseling services).

7.7 Collaboration with CTSA for Site Recruitment

Site recruitment will explore opportunities to partner with the NIH-funded Clinical and Translational Science Award (CTSA) consortium. CTSA institutions work to transform local, regional, and national environment to increase the efficiency and speed of clinical and translational research. Potential opportunities for collaboration between CTN-0067 and affiliated CTSA include CTSA assistance with community-based recruitment and/or some aspects of study implementation.

8.0 OUTCOME MEASURES

8.1 Primary Outcome Measures

The *primary outcome* variable for CTN-0067 CHOICES scale-up study is HIV viral suppression. HIV viral suppression is defined as an HIV-1 RNA \leq 200 copies/ml at 24 weeks. We are aware that, for participants on therapy, the goal of antiretroviral therapy is achieving a viral load “below the limit of detection of the assay” which currently is usually $<$ 40 copies/ml. However, we have chosen to define “suppression” for this study as less than or equal to 200 copies/ml to be consistent with the January 2011 Guidelines for the Use of Antiretroviral Agents in HIV-1-Infected Adults and Adolescents [92]. The rationale for this definition is to avoid the influence of “blips” in HIV RNA viral load which commonly occur at levels between 40 and 200 copies/mL using current PCR assays and which are of limited clinical significance [125, 126].

8.2 Secondary Outcome Measures

1) Secondary HIV outcomes:

- a. VACS Index. Change in VACS Index at 24 weeks compared with randomization. (score; derived from screening and week 24 laboratory and demographic data).
- b. CD4 Count. Change in CD4 count at 24 weeks compared with randomization (count; laboratory assay).

2) Engagement in HIV Care:

- a. ART Prescribed. Proportion of participants prescribed ART within 24 weeks following randomization (binary; medical record abstraction).
- b. ART Adherence. Proportion of participants taking 100% of prescribed ART doses in the past month at 24 weeks for those prescribed ART at any point during the 24 week trial (binary; self-reported VAS medication adherence measure).
- c. Retention in HIV Care. Proportion of participants with at least 1 HIV primary care visit in the past 12 weeks, measured at week 24 (binary; medical record abstraction).
- d. HIV Risk Behaviors. Past 30 day injection drug use, unprotected sex, multiple sexual partners as measured by the RAB at week 24 (binary; self-report).
- e. Quality of life. Past 30 day health-related quality of life as measured by EQ-5D at week 24, compared to baseline.

3) ART Adherence Mediation Variables:

- a. Days of Opioid Use. Number of days of opioid use since baseline, as measured by Timeline Follow Back (TLFB) at 24 weeks (count; self-report).
- b. Opioid Abstinence. Past 30 day opioid abstinence (by Addiction Severity Index (ASI)-lite self-report, Time-Line Follow-Back (TLFB) and urine drug screen (UDS) confirmation) in the final 30 days of the 24 week trial (binary; self-report + UDS).

9.0 STUDY PROCEDURES

9.1 Duration of Participant Study Procedures

9.1.1 Pre-screening

Individuals will be approached by study staff in HIV clinic settings or referred to study staff by HIV clinical care and outreach teams. Study staff will provide a brief verbal overview of the study to the individual and provide written information regarding XR-NTX. Individuals will provide verbal consent and HIPAA Authorization/Waiver as necessary for pre-screening and will be asked to complete the Pre-Screening Interview. This verbal consent and HIPAA Authorization/Waiver will only apply for the Pre-Screening visit. The Pre-Screening Interview will elicit information about the potential participant's demographics and drug use. The Pre-screening informed consent, HIPAA Authorization/Waiver (if necessary), and pre-screening interview will take approximately 5, 5, and 10 minutes to complete, respectively. Individuals who undergo pre-screening will be captured on the Pre-Screening Log.

